## 4.2 Scientific Rationale for Study Design

### Rationale for High-Frequency Computerized Test Administration

Over the past decade, successive external and internal studies have progressively evaluated the ability of repeated, high-frequency computerized cognitive testing to identify potential treatment effects of pro-cognitive compounds in small study populations over a limited treatment duration. Based on these studies, the high-frequency testing methodology is believed to improve measurement precision with enhanced sensitivity to detect cognitive change. Overall, the idea of high frequency testing is based on the premise that patients with AD pathology typically have significant fluctuations in cognitive performance over time, and even on a daily basis. As a result, solitary assessments of cognition conducted several months apart (as typically done with the ADAS-Cog, for example) may not accurately assess a patient's true mean cognitive baseline or their true mean cognitive performance after several months of treatment with a symptomatic pro-cognitive compound. However, if cognitive testing could be conducted more frequently, individual test variability could have less impact on overall performance, supporting more accurate determination of true baseline cognition and providing more reliable results of potential treatment effect.

Previously, AstraZeneca conducted a study (CogMemo) in collaboration with Cogstate Ltd. in patients with mild to moderate AD, in which a standardized computerized test battery (Cogstate) as well as a standardized paper/pencil battery (ADAS-Cog and the NTB) were administered to participants multiple times on a monthly basis to obtain an assessment of baseline cognition, followed by repeated testing around the time of efficacy at 4, 8 and 12 weeks of treatment with donepezil. Group differences were detected after 8 and 12 weeks of treatment when applying individual Cogstate tests, but not using more conventional cognitive assessments, such as ADAS-Cog and the NTB. These results seemed to support the idea that providing a standard, computerized battery with multiple forms (to minimize practice and learning effects after repeated administration) with the potential for reduced examiner-induced variability, could improve the ability to detect a treatment signal in a smaller population over a short duration of treatment. In particular, the OCL, a measure of visual learning in the Cogstate Battery was able to demonstrate a statistically-significant treatment effect following monthly administration.

A follow-up Merck experimental medicine study (MK-0000-318) conducted in conjunction with Cogstate Ltd. included repeated testing of increased frequency (~ 5 in-home test administrations over a 7-day test period, conducted at baseline and repeated monthly after 1, 2 and 3 months of treatment) in participants with MCI and participants with mild AD treated with donepezil versus placebo. Cogstate tests were conducted in the presence of a trained testing supervisor in the participants' homes in order to ensure a consistent test environment, support participant motivation, and assist with technical challenges. The primary objective of the study was to evaluate inter- and intra-subject variability following repeated administration of the Cogstate battery, particularly the OCL test. The secondary objective of the study was to evaluate a potential treatment effect among donepezil-treated participants, comparing change in performance on the OCL test after 12 weeks of treatment with OCL performance at baseline. The study achieved both objectives, demonstrating low inter- and

intra-subject variability and a relative improvement in OCL performance within donepezil-treated participants following 12 weeks of treatment. These results further supported the idea that high-frequency computerized test administration improves the potential to detect a symptomatic pro-cognitive effect in smaller participant populations over a limited duration of treatment. However, there were some limitations with the study. First, while 36 total participants were included in the study, only a limited number of participants (N=6) were allocated to treatment with placebo, precluding extensive analysis of treatment effects between donepezil- and placebo-treated participants. Second, operational challenges of locating treatment-naïve participants with MCI and AD combined with difficulties with locating site staff willing to travel to participants' homes and subsequent coordination of home supervisor/participant scheduling led to extended recruitment timelines and required 26 months to complete the study.

The current study will build on these prior evaluations and respond to previously- identified challenges. Like the CogMemo study and MK-0000-318, it will include a limited number of study participants in an affected patient population of participants with MCI and mild AD. Like the CogMemo and MK-0000-318 studies, this study will include high-frequency repeated administration of a computerized test battery (Cogstate). However, in contrast to MK-0000-318, in which supervised testing was conducted in participants' homes, this study will conduct cognitive testing in the clinic. This shift is hypothesized to help standardize the test environment and mitigate sources of variability in at-home testing scenarios that may impede determination of a potential treatment effect signal. The recruitment and retention benefit of ensuring trained test administrators could engage participants directly in their homes was also not deemed sufficient rationale for continuing to pursue this approach due to its overall operational complexity.

The overall study duration for an individual participant will be approximately 15-19 weeks from Screening to Post-Study Visit, compared with 24 weeks for MK-0000-318.

### **Rationale for Study Treatment Duration**

While the MK-0000-318 study evaluated the Cogstate effects of 12 weeks of treatment with donepezil (including 2 weeks of treatment with 5 mg PO daily, followed by 10 weeks of treatment with donepezil 10 mg PO daily), post-hoc analyses of donepezil treatment effect in the study data indicate that the earliest potential treatment effect may be seen following a minimum of 6 total weeks of treatment with donepezil, including 2 weeks treatment with donepezil 5 mg PO daily followed by titration up to 10 mg PO daily for 4 weeks. Additional positive treatment efficacy was observed following longer durations of donepezil treatment (10- and 14- weeks). This study will include an 8-week donepezil treatment duration, including an initial 2 weeks treatment with donepezil 5 mg PO daily followed by titration up to 10 mg PO daily for 6 weeks. The rationale for this treatment duration is to minimize the overall exposure for participants in the study, but also to ensure sufficient treatment duration (i.e. > 6 weeks, based on MK-0000-318 findings) to maximize probability of observing efficacy.

## **Rationale for Test Frequency**

Subjects will participate in repeated test assessment periods approximately every two weeks after initiating treatment. The two-week interval was selected based on the t1/2 of donepezil, which is approximately 70 hours and as a result is expected to reach steady-state concentrations after approximately two weeks of daily dosing. Assessments conducted after Week 2 in the Treatment Period are expected to assess potential treatment effect once steady-state PK is reached for donepezil 5 mg PO daily; assessments at Week 4 in the Treatment Period will assess potential treatment effects once steady-state PK is reached for donepezil 10 mg PO daily; and assessments at Week 8 will assess treatment effects at a timepoint following the minimal treatment duration following which a treatment effect signal was observed in MK-0000-318.

As in MK-0000-318, participants in this study will complete multiple test administrations for each test period (Weeks 2, 4, 6, 8, 10). The number of repeated assessments is based on the minimum number of daily assessments required to ensure adequate test reliability and treatment effect response as estimated from the MK-0000-318 data.

### **4.2.1 Rationale for Endpoints**

#### **4.2.1.1 Efficacy Endpoints**

There are no direct efficacy assessments in this study.

#### **4.2.1.2 Safety Endpoints**

Safety for all participants will be assessed throughout the study by monitoring for clinical AEs, including physical/neurological examinations, C-SSRS, VS, and laboratory safety tests (serum chemistry, hematology, and urinalysis).

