| Study Visit Window (Days)                              | (-30) c | Within 4d prior d                        |   | AM                                   | PM              | AM     |                | PM              | AM |                 | PM              | +3 |    | +3              |    | +3 |                 | +3 |                         |       |  |  |  |  |  |
| Targeted Neurological Examination                      | X                  |   |   |                                      |                 |        |                |                 |    |                 |                 |    |    |                 |    |    |                 |    |                         |       |  | Section 8.3.2 and Appendix 9. Mental status module is covered by MMSE. |  |  |  |
| Vital Signs (Heart Rate, Blood Pressure)               | X                  |   |   |                                      |                 |        |                |                 |    |                 |                 |    |    |                 |    |    |                 |    |                         |       | X  | Section 8.3.3  |  |  |  |
| Respiratory Rate                                       | X                  |   |   |                                      |                 |        |                |                 |    |                 |                 |    |    |                 |    |    |                 |    |                         |       |  | X  |  |  |  |
| Body Temperature                                       | X                  |   |   |                                      |                 |        |                |                 |    |                 |                 |    |    |                 |    |    |                 |    |                         |       |  | X  |  |  |  |
| 12-lead ECG n                               | X                  |   |   |                                      |                 |        |                |                 |    |                 |                 |    |    |                 |    |    |                 |    |                         |       |  |  | Section 8.3.4  |  |  |

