| AE/SAE review  | X                  | -----X  |   |                                      | X               | -----X |                |                 | X  | -----X          |                 |    | X  | -----X          |    |    |                 |    |                         |       |  |  |  |  |  |
| C-SSRS Screening                                       | X                  |   |   |                                      |                 |        |                |                 |    |                 |                 |    |    |                 |    |    |                 |    |                         |       |  |  | Section 8.3.6  |  |  |
| C-SSRS Since Last Visit                                |                    |   |   | X                                    |                 |        | X              |                 |    | X               |                 |    | X  |                 | X  |    |                 | X  |                         | X     | X  | X  | Section 8.3.6  |  |  |

| Study Period:  | Screening                         |   |   |                  | Single-Blind          |   |                | Double-Blind          |   |                 |                       |    |    |                       |    |    |                       |    | Post-study a | Notes |  |
|--|-----------------------------------|---|---|------------------|-----------------------|---|----------------|-----------------------|---|-----------------|-----------------------|----|----|-----------------------|----|----|-----------------------|----|-------------------------|-------|--|
|  | n/a                               | 1   |   |                  | 2                     |   |                | 3                     |   |                 | 4                     |    |    | 5                     |    |    | 6                     |    |                         |       | n/a  |
| High Frequency Testing Period b                                     | 1 c                    | 2 d                                  | 3 | 4 e   | 5                     | 6 | 7 f | 8                     | 9 | 10 g | 11                    | 12 | 13 | 14                    | 15 | 16 | 17                    | 18 | 19                      | 20    |  |

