## 8 STUDY ASSESSMENTS AND PROCEDURES

- Study procedures and their timing are summarized in the SoA.
- Adherence to the study design requirements, including those specified in the SoA, is essential and required for study conduct.
- The investigator is responsible for ensuring that procedures are conducted by appropriately qualified (by education, training, and experience) staff. Delegation of study site personnel responsibilities will be documented in the Investigator Trial File Binder (or equivalent).

- All study-related medical decisions must be made by an investigator who is a qualified physician.
- All screening evaluations must be completed and reviewed to confirm that potential participants meet all eligibility criteria. The investigator will maintain a screening log to record details of all participants screened and to confirm eligibility or record reasons for screening failure, as applicable.
- Procedures conducted as part of the participant's routine clinical management (eg, blood count) and obtained before signing of ICF may be utilized for screening or baseline purposes provided the procedure met the protocol-specified criteria and were performed within the time frame defined in the SoA.
- Additional evaluations/testing may be deemed necessary by the investigator and or the Sponsor for reasons related to participant safety. In some cases, such evaluation/testing may be potentially sensitive in nature (eg, HIV, Hepatitis C), and thus local regulations may require that additional informed consent be obtained from the participant. In these cases, such evaluations/testing will be performed in accordance with those regulations.

The maximum amount of blood collected from each participant over the duration of the study will not exceed approximately 151 mL (Appendix 8).

Repeat or unscheduled samples may be taken for safety reasons or for technical issues with the samples.

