## **8.3 Safety Assessments**

Details regarding specific safety procedures/assessments to be performed in this study are provided. The total amount of blood/tissue to be drawn/collected over the course of the study (from Screening to Poststudy visits), including approximate blood/tissue volumes drawn/collected by visit and by sample type per participant, can be found in Appendix 8.

Planned time points for all safety assessments are provided in the SoA.

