| Sorting (D-KEFS)   | X  | X   |
| 15-min Break a  | X  | X   |
| Verbal Fluency Test (D-KEFS) c  | X  | X   |
| Twenty Questions (D-KEFS)  | X  | X   |
| AE=adverse event; D-KEFS = Delis-Kaplan Executive Function System; FCSRT = Free and Cued Selective Reminding Test; WAIS = Wechsler Adult Intelligence Scale
a Short break to stretch or visit restroom facility; participant should not be given reading materials or become engrossed in other activities during this time.
b No other cognitive assessments can be performed during the 20-30 min interval between Trial 3 of Free and Cued Recall and the start of Delayed Recalled portion of the FCSRT. The participant will be given another short break during this time.
c For the Verbal Fluency Test, only the letter fluency and category fluency tasks will be administered. |    |     |

Note that the LFCB assessments may be split across 2 days (i.e. Visits 3-4; and Visits 18-19) to decrease participant burden. The rater should ensure consistency in the administration of the LFCB during the course of the study. If the screening/pre-treatment LFCB was performed over 2 days for an individual participant at Visits 3-4, then the LFCB scheduled for the later timepoint (i.e. Visit 18) should also be consistently split across 2 days (i.e. Visits 18-19). [Table 7](#) is a recommendation of how the LFCB assessments should be conducted across 2 study visits.

Table 7 Recommended Order and Timing of Procedures at Visits 3-4 and 18-19 if Splitting Visits

| Procedure  | Visit 3 Split Visit a |    | Visit 18 Split Visit a |     |
|--|----------------------------------|----|-----------------------------------|-----|
|  | V3                               | V4 | V18                               | V19 |
| Assess concomitant medication use and AE(s) b | X                                | X  | X                                 | X   |
| Review Study Intervention Dosing Diary                   |                                  |    | X                                 | X   |
| Cogstate Battery   | X                                | X  | X                                 | X   |
| 15-min Break c                                | X                                | X  | X                                 | X   |

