| FCSRT d                                       | X                                |    | X                                 |     |
| WAIS-IV Coding   | X                                |    | X                                 |     |
| Sorting (D-KEFS)   | X                                |    | X                                 |     |
| Verbal Fluency Test (D-KEFS) e                |                                  | X  |                                   | X   |
| Twenty Questions (D-KEFS)                                |                                  | X  |                                   | X   |
| Blood Collections f                           |                                  | X  |                                   | X   |

AE=adverse event; D-KEFS = Delis-Kaplan Executive Function System; FCSRT = Free and Cued Selective Reminding Test; WAIS = Wechsler Adult Intelligence Scale

a Procedures for Visit 3 and Visit 18 split across 2 days, with some procedures conducted at Visit 4 and Visit 19, respectively.

b Includes C-SSRS (at selected timepoints per Section 1.3 SoA)

c Short break to stretch or visit restroom facility; participant should not be given reading materials or become engrossed in other activities during this time.

d No other cognitive assessments can be performed during the 20-30 min interval between Trial 3 of Free and Cued Recall and the start of Delayed Recalled portion of the FCSRT. The participant will be given another short break during this time.

e For the Verbal Fluency Test, only the letter fluency and category fluency tasks will be administered.

f Blood for Genotyping/PK/Biomarkers (if applicable as per Section 1.3 SoA)

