### 10.8 Appendix 8: Blood Volume Table

|  | Screening | Randomization (Visit 4) | Treatment Period (Visits 10, 13, 19) | Poststudy (Visit 20) | Total Collections | mL Per Collection | Total mL/ Test |
|--|-----------|-------------------------|--------------------------------------|----------------------|-------------------|-------------------|----------------|
| Chemistry (including TSH, Vitamin B12, & FSH at Screening)   | 1         |                         |                                      | 1                    | 2                 | 8                 | 16             |
| Hematology   | 1         |                         |                                      | 1                    | 2                 | 3                 | 6              |
| Folate, MMA, RPR   | 1         |                         |                                      |                      | 1                 | 8                 | 8              |
| Homocysteine   | 1         |                         |                                      |                      | 1                 | 3                 | 3              |
| HIV/Hepatitis Screen   | 1         |                         |                                      |                      | 1                 | 6                 | 6              |
| Blood for Plasma Donepezil Assay   |           |                         | 3                                    |                      | 3                 | 3                 | 9              |
| Blood for Exploratory Plasma Biomarkers for AD Diagnosis   |           | 1                       | 1                                    |                      | 2                 | 20                | 40             |
| Blood for APOE genotyping  |           | 1                       |                                      |                      | 1                 | 4                 | 4              |
| Blood for Planned Genetic Analysis   |           | 1                       |                                      |                      | 1                 | 8.5               | 8.5            |
| Total Blood Volume for Participant   |           |                         |                                      |                      |                   |                   | 100.5          |

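### No heart rate or blood pressure is scheduled while participants take double-blind donepezil, although Section 4.2.1.2 lists vital signs as part of safety assessment throughout the study

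*Combined protocol and SAP*

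**What the plan says.** Section 4.2.1.2 describes safety monitoring as continuous and names its components: "Safety for all participants will be assessed throughout the study by monitoring for clinical AEs, including physical/neurological examinations, C-SSRS, VS, and laboratory safety tests". It gives no visits. Section 8.3 says where the visits are set: "Planned time points for all safety assessments are provided in the SoA".

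The SoA (Section 1.3) schedules these components as follows:

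- The row "Vital Signs (Heart Rate, Blood Pressure" has one mark at Visit 1 and one at the far right of the row, read as poststudy (Visit 20).
- The physical examination row shows the same two positions.
- The neurological examination is marked at Visit 1 only. The ECG is also screening only, or a report from the preceding 3 months.
- Haematology, chemistry and urinalysis are at screening and poststudy. In Appendix 8, the line "Chemistry (including TSH, Vitamin B12, & FSH at Screening" counts one collection at screening, none in the treatment period and one poststudy.
- "C-SSRS Since Last Visit" recurs through the double-blind period, as does adverse event review.

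Exclusion 9 lists sick sinus syndrome, heart block and a screening heart rate below 50 bpm as relative contraindications to donepezil. Section 6.6 has the investigator judge tolerability at Visit 10 and raise the dose from 5 mg to 10 mg. Section 4.3 acknowledges that this 2-week step is shorter than the label recommends.

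**The concern.** The protocol treats slow heart rate as a reason not to give donepezil, checks it once before exposure, and then schedules no further check until the drug has largely gone. Adverse event review and C-SSRS do run on treatment, but neither would reveal slowing that causes no symptoms. The decision to double the dose at Visit 10 is taken with no scheduled heart rate since Visit 1, and none follows while the participant is on 10 mg.

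What is at stake is participant safety monitoring and the accuracy of Section 4.2.1.2. The statistical decision rule is not affected. Section 4.2.1.3 also says donepezil concentrations are collected to help explain effects on safety endpoints, but there is no scheduled on-drug heart rate or blood pressure to set beside them.

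**Working it through.** The plan states no figure to reproduce. The check is a reading of the schedule followed by date and half-life arithmetic.

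**Reading the SoA rows.** Number the cells so that the row label is 0, Visit 1 is 1 and Visit 20 is 20. In the machine-readable table:

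- Heart rate/blood pressure and physical examination: marks at cells 1 and 21. Cells 2 to 20 (19 cells, including Visits 8 to 19) are blank.
- Respiratory rate, temperature, haematology, urinalysis and chemistry: marks at cells 1 and 22.
- Neurological examination and ECG: cell 1 only.

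The columns are shifted, so the poststudy place of the second vital-signs mark is inferred. Haematology and chemistry show the same pattern one cell over, and for those Appendix 8 and the fasting rule in Section 5.3.1 confirm screening and poststudy. Vital signs have no such independent check. A shift moves marks but does not delete them. If the second mark belonged to Visit 19, the on-drug count would be 1 of 12, still with nothing around the dose increase.

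Table 7 ("Recommended Order and Timing of Procedures at Visits 3-4 and 18-19 if Splitting Visits") is consistent. For Visits 18 and 19 it lists adverse event review with the footnote "Includes C-SSRS (at selected timepoints per Section 1.3 SoA", diary review, cognitive tests and blood collection, but no vital signs. This is weak support, because the table only recommends an order of procedures.

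**Scheduled on-drug readings.** 0 of the 12 visits from 8 to 19.

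**Age of the last scheduled heart rate at Visit 10** (SoA days, no Day 0, before visit windows).

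- Day -32 to Day 15: 32 + 14 = 46 days.
- Using the 3 to 7 week screening range instead: Visit 4 (Day -14) to Day 15 is 14 + 14 = 28 days, so 21 + 28 = 49 to 49 + 28 = 77 days. The upper end is reduced if Visit 1 is split for washout, because Section 8.10.1 suggests taking vital signs in its final portion.

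**Gap between the two scheduled readings.** Day -32 to Day 70: 32 + 69 = 101 days.

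**Drug remaining at the poststudy reading.** The last dose is the evening before Visit 19 (Day 56), Visit 20 is Day 70, and the half-life is about 70 h (Section 2.2.1). The interval is 324 to 336 h. With first-order decline, fraction remaining = 0.5^(hours/70):

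- 324/70 = 4.63 half-lives, leaving 4.0%.
- 336/70 = 4.80 half-lives, leaving 3.6%.

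**With four added readings** (Visits 10, 13, 16 and 19; Days 15, 29, 43 and 57): 4 of 12 visits. If all 36 participants attend, 36 × 4 = 144 readings, of which 24 × 4 = 96 are on donepezil and 12 × 4 = 48 on placebo. From Visit 10 to Visit 20 the gaps are 14, 14, 14 and 13 days.

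**The case against.** The strongest reply is that Section 4.2.1.2 is a one-sentence rationale. Its claim of continuity can be read as attaching to adverse event monitoring, which does run on drug, and a site that follows the SoA makes no error. Donepezil is a marketed drug used within its recommended dose. Section 2.2.1 does not list bradycardia among the adverse events it names. Section 4.3 supports the 2-week step: of 30 participants titrated in the earlier sponsor study, 4 stopped for adverse events, none directly attributed to the titration. Entry already screens out slow heart rate and heart block. Section 8 also allows extra checks: "Additional evaluations/testing may be deemed necessary by the investigator and or the Sponsor", and Appendices 2 and 3 contain similar provisions.

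Much of this stands. The documents contain no event rate, so the benefit cannot be quantified, and nothing shows the titration to be unsafe. The wording mismatch alone would be a minor edit. But the added checks are discretionary or event-driven, and symptom-free slowing prompts neither. Section 8.10.5 lets the timing of vital signs change but not the number of procedures, so it does not supply the missing readings.

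Two further points stand as small costs. A dose held because of a Visit 10 reading would remove that participant from the primary analysis under Section 6.6, and such holds could fall mainly on the donepezil arm. A reading that responds to drug might also hint at allocation to a blinded investigator. The first applies to any tolerability hold already foreseen in the plan. For the second, taking the reading after the Cogstate battery keeps it out of that day's computerised testing.

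**Conclusion.** The point holds. Heart rate and blood pressure are scheduled at 0 of 12 double-blind visits. The last scheduled value is about 46 days old when the dose is doubled (49 to 77 days over the stated screening range, less with a split Visit 1). The only later value is taken with about 3.6 to 4.0% of drug remaining and cannot stand in for an on-treatment reading.

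This rests on reading the displaced vital-signs mark as poststudy, on a 70 h half-life with first-order decline, and on day counts without a Day 0. The figures describe scheduling, not risk. The change is worth making because it is cheap and addresses a risk that the protocol itself screens for; it is not urgent. Heart rate and blood pressure are a screen and cannot diagnose heart block.

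**What to change.** Add resting heart rate and blood pressure to the SoA at Visits 10, 13, 16 and 19, by the method in Section 8.3.3.1.

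- Take the readings after the Cogstate battery, as SoA footnote p requires, and at Visit 19 after any low-frequency cognitive tests split to that day.
- At Visit 10, have the investigator review the reading before deciding on titration. Any action threshold is for the sponsor to set; the 50 bpm in Exclusion 9 is available. Section 6.6 already provides for sponsor consultation when a participant is judged unsuitable for titration.
- Reword Section 4.2.1.2 to match: adverse event review and C-SSRS throughout; heart rate and blood pressure at screening, these four visits and poststudy; physical examination and laboratory tests at screening and poststudy; neurological examination at screening.

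No on-treatment ECG, neurological examination or laboratory test is needed for this.

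The cost is a protocol amendment plus, at each of four visits already attended, at least 10 minutes of semi-recumbent rest and a reading of 2 to 5 minutes (assumed). That is 12 to 15 minutes per visit, 4 × 12 = 48 to 4 × 15 = 60 minutes per participant, and 36 × 48/60 = 28.8 to 36 × 60/60 = 36 hours over the trial. There is no new visit and no new type of procedure.
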